The ReWalk powered exoskeleton has safeguards built within the device to prevent or minimize injury to the user. The system can detect if there is a mechanical or electrical problem and automatically causes the device to remain in the standing position, preventing the user to walk in the system. The only movement the device will be able to do is sit down so that the user can be removed from the system safely. If there is a mechanical error while in the sitting position, the device will not allow the user to stand in the system, and there will be a sound alerting the person that there is a problem. If there is a sudden loss of power while standing or walking, there is a safety mechanism that will stiffen the joints of the exoskeleton passively and cause the joints to rotate slowly so that the person can have a “graceful” collapse to the floor without causing them harm. The “graceful” collapse function allows time for a protective response with the arms to reach for the ground. The ReWalk exoskeleton is instrumented with two power sources; one main battery which has power for up to 4 hours of continuous walking and an additional back up battery which has power for up to an additional 30 min of walking. The participant, companion and study team members will be instructed to ensure that the power source of the system is fully charged prior to any use of the ReWalk.

To prevent tripping over obstacles, the areas used for the sit-to-stand, stand-to-sit, walking, and stepping will be checked before and during each session to be free of any obstacles and water on the floor. There are risks associated with anticoagulation therapy if a participant were to fall and hit their head. It will be strongly recommended that participants receiving anticoagulation therapy wear a helmet during use of the exoskeleton. To prevent a potential fall, participants will not be progressed to walking until they have mastered the basic skills set. Additionally, all participants will be spotted by at least one study team member (and/or their companion once trained) while using the ReWalk and never left unattended.

Additional efforts to minimize the risk of fracture will be done by excluding those veterans with BMD in the extremely low range. Measurement of the BMD is part of the screening and eligibility criteria for participation in this study. Those potential participants who have low bone mass will

be excluded from the study (please see inclusion/exclusion criteria for details). There is risk associated with radiation exposure. The BMD assessment has a small amount of radiation exposure from the DXA scan. Measurements of two areas for BMD (hips and knees) will be performed one time for screening. The total body scan will be performed at baseline and will be repeated three additional times during the study. The following is a list of radiation exposure associated with each scan area obtained in this study.

Scan Type	Entrance Dose	Effective Dose	Scan Time
Hips	329 μ Gy	12.3 μ Sv	212 sec
Knee	34 μ Gy	unavailable	54 sec
Total Body	6 μ Gy	8.62 μ Sv	739 sec
Foot x-ray	unavailable	2.0 μ Sv	<1 sec

Values of radiation absorption (i.e. Effective Dose) for knee scans do not exist at this time. However, considering both the amount of radiation emitted and the scan time is lower than that of the other scans, the absorbed amount should also be lower than that of the hips (GE Medical Systems, Madison WI). The estimated sum quantity of radiation exposure from all of these DXA measurements combined is <35 μ Sv of absorbed radiation. This measurement is minimal even when compared to a routine chest x-ray which has an approximate dose of 60 μ Sv. In addition, the average person in New York City receives approximately 3000 μ Sv/year. Therefore, these tests would need to be repeated 85 times to receive an equivalent dose.

H. Emergency Care Plan

This study will be conducted in the VA hospitals at fifteen sites, in the CBOCs under the same FWA as the sites, or in the participant’s home/community. During site visits and when training is conducted in the VA hospitals, the VA Hospital’s emergency department would be called in the event of a medical emergency. If a participant is injured as a result of this study, the hospital site will be responsible for their medical care and the costs of this care. If a participant is seriously injured in their home or community environment during training or when using the device in their home, the study team and the participant (or their companion) will be instructed to call 911.

I. Potential Benefits

The information gained from this study may be scientifically useful to the field of SCI medicine.

The individual may experience improvements in QOL, but this is not guaranteed. An additional benefit of this study is to share the knowledge gained with the SCI Clinical Services in the VA system.

The participant will have both the participant version of the Informed Consent and HIPAA forms to sign. The Companion will have the option to sign the companion version of the Informed Consent and HIPAA authorization or provide assent over the phone. Only demographic information and AE / SAE information will be collected on the companions. A sample version of these five documents may be viewed in the Human Rights section.

XIX. TRANSITION OF PARTICIPANTS

The long-term aim of this study is to acquire information and share the new found knowledge and insights with the clinical SCI Services. This information will assist the SCI Services to gain the necessary skills to develop and provide exoskeletal-assisted walking programs in-house with the anticipation of providing home prescription to interested and eligible Veterans and military members with SCI. It should be noted that before clinical staff can train patients at their facilities in the use of the exoskeleton, they will receive specific instruction/training in the use of the device.

In addition to having a truly immediate translation to clinical care, our study will actually make possible the clinical use of the exoskeleton by training local professional staff to become sufficiently skilled in the training of Veterans and military members with SCI who wish to use this technology for upright ambulation. In summary, clinical staff at the study sites will have the opportunity to directly participate in exoskeletal training, which will provide hands-on experience that will be readily transferrable to clinical care. This study will provide important clinical information, such as who are the best candidates for home use of an exoskeleton, the average number of sessions needed to pass the advanced skills test, the level and completeness of SCI that is related to successful use of the device, how often and in what locations the exoskeletons should be used, and any unexpected adverse events or serious adverse events, if they should occur, associated with home use. The prosthetics and orthotics departments will gain the opportunity to learn about the system and how to fabricate additional padding, if needed, for participants in addition to setting up contracting for purchasing these types of devices. There are other exoskeletons which will become available. The experience that the facilities gain from participation in this study will be a basis to identify the important features these new systems may offer to improve clinical care provided to veterans with SCI. Perhaps most importantly for the

clinical services, is the question of there being unexpected adverse events or serious adverse events associated with home use as well as how much is this device actually being used in the home/community environment.

XX. IMPACT OF THE SARS-COV-2 (COVID-19) PANDEMIC ON VETERANS WITH SPINAL CORD INJURY

This section has been added to the protocol to identify the impact of the COVID-19 pandemic on the screened participants from CS #2003. The questions to be asked are unrelated to the original research design and outcomes of CS #2003. A baseline questionnaire will be completed with screened participants as well as a follow-up questionnaire and a blood draw. These additions are at no additional cost to the study. All costs will remain budget neutral within each site. Although a budget for each site will be provided, it is understood that each site will cover these costs within the approved budget for their site.

A. Background

In the United States (US), the first case of the 2019 novel coronavirus disease (COVID-19), caused by the severe acute respiratory syndrome SARS-CoV-2 virus, was reported on January 19, 2020

VA Site Location	# of Positive Cases	# of Deaths
1 Boston	12,511	618
2 Houston	10,995	221
3 Long Beach	1,582	73
Los Angeles	46,018	2,116
4 Palo Alto	2,602	139
San Francisco	2,386	40
5 Richmond	1,546	118
6 Tampa	1,939	72
7 St. Louis	4,690	387
8 Dallas	8,998	211
9 Minneapolis	7,168	539
10 Milwaukee	6,535	257
11 Albuquerque	1,347	68
12 Augusta	529	18
13 Bronx	43,252	3,473
New York City	203,569	20,740
14 Cleveland	3,963	217
15 San Antonio	2,449	69

(Holshue, et.al., NEJM March 2020). As of May 26, 2020, the US had 1,697,361 confirmed cases with 99,462 deaths and in the Veteran’s Affairs Health system, there had been 13,327 positive cases and over 1,133 deaths. The numbers of positive cases and deaths in the cities where the VA CS #2003 study sites are located is provided (Table 20).

There is limited information available on how Veterans with SCI have been affected by COVID-19. The most severe and direct negative impact for Veterans with SCI would be to contract COVID-19. Indirect negative impacts may also stem from the loss of caregiver or home attendant services, difficulty accessing routine healthcare, maintaining

wheelchairs, assistive and/or adaptive equipment, and other inconvenient and potentially harmful disruption of services that may be occurring. Positive indirect benefits may also be occurring, such as increased access to internet-based activities.

B. Rationale

Veterans with SCI are often immunosuppressed and have chronic health conditions (e.g. cardiovascular disease, respiratory compromise, metabolic disease including diabetes mellitus) that place them at a potentially higher risk of complications and more severe symptoms should they contract COVID-19. Additionally, individuals with SCI may be debilitated from poor nutrition, experience chronic pressure injuries with or without osteomyelitis, have concurrent respiratory infections, and experience frequent urinary tract infections (UTI). Of note, individuals with higher cord lesions who have difficulty clearing secretions from their lungs because of an impaired or absent cough due to respiratory muscle weakness from paralysis are at a higher risk of developing pneumonia and its complications. The signs and symptoms of COVID-19 may be different in individuals with SCI than the general population. For example, the high fevers characteristic of COVID-19 in the general population may not be observed in persons with tetraplegia, who experience lower core body temperatures, thereby requiring a different definition of fever for symptom surveillance and clinical diagnosis. Also, the common feeling reported of chest pressure may be absent in those who are insensate in this area. Persons with respiratory compromise, may experience shortness of breath earlier in the course and decline more rapidly, an indication for earlier admission and closer surveillance.

In the Veterans Health Administration (VHA) and the Spinal Cord Injury and Disease (SCI/D) National Registry, there are 17,806 Veterans with SCI. It is not known how many Veterans with SCI are, or will be, directly infected by this virus, nor the severity of their symptoms and survival rates. However, it is anticipated that, due to their high risk of immunodeficiency and other comorbidities, the occurrence may be higher, with the potential for more severe symptoms and greater mortality than in the general population.

Additionally, of great concern, is the anecdotal report of loss of services, including routine medical care for non-COVID-related conditions (i.e. pressure injuries, urinary tract infections, etc.), loss or interruption of caregiver services, and wheelchair or assistive devices repair options, that has been an unfortunate consequence of the pandemic. [name], President and CEO of United Spinal Association, Inc. (a membership of 58,000 nationwide which includes about 1500

Veterans with SCI) stated on March 30, 2020: *“Homecare workers, always in short supply, are staying home watching their kids, self-isolating because of potential exposure--or exposure, and traveling via public transportation to patients and potentially exposing them. More than ever, it has become obvious that adequate homecare services are a fundamental necessity of the SCI community in order to stay out of nursing homes and hospitals.... And many are replacing caregivers with family members out of fear they will become infected from the caregiver”.*

The VA Cooperative Study Program’s CS #2003 is able to use the existing study staff to conduct a baseline survey/medical chart review, a follow-up survey and a blood draw. The survey would be used to determine the participant-reported direct medical effects of COVID-19 (with the use of the medical record when and if information is available) and the indirect psychosocial and environmental impacts of COVID-19 on Veterans with SCI who have been screen-consented for CS #2003. This knowledge would provide a “snapshot” of what is occurring across the nation in Veterans with SCI and will enable us to plan to meet the immediate needs of the Veteran SCI community as the course of the pandemic becomes known across the US. This information will be important to the VHA and the SCI/D National Service to be able to better prepare for future pandemics and other natural disasters. Immediate benefit may be the identification of Veterans with SCI who are in urgent need of services. This information would be relayed back to the medical center providers. As of the date of the administrative hold for CS #2003 on March 16, 2020, more than 400 Veterans with SCI had been screened for participation across 15 VA sites. A list of the number screened by site is provided (Table 21).

	Site	Count
1	Boston	34
2	Houston	28
3	Long Beach	48
4	Palo Alto	37
5	Richmond	35
6	Tampa	41
7	St. Louis	34
8	Dallas	31
9	Minneapolis	34
10	Milwaukee	36
11	Albuquerque	10
12	Augusta	16
13	Bronx	11
14	Cleveland	15
15	San Antonio	13
Total Screened		423

The infrastructure for VA CS #2003 is in place with funding on stations through September 30, 2020 and a full budget (4 staff per site at 14 sites) is requested for fiscal year (FY) 21 (Houston was withdrawn as a site in 2018, but those screened participants can be contacted by the San Antonio site staff). VA CS #2003 was put on a voluntary administrative hold on March 16, 2020. CS #2003 study staff will be trained to conduct the surveys and medical chart reviews while other clinical research is on hold and to continue to conduct the surveys once the administrative hold has

been lifted. The administrative hold has been lifted for the COVID-19 survey and blood draw.

The initial phone or in-person survey serves to capture COVID-19 information from the Veterans with SCI themselves that may not be in the medical record. This survey includes SCI-specific questions related to demographics, neurological characteristics and any loss of services during the pandemic. For example, information will be recorded such as the amount of assistance provided before the pandemic, the loss or reduction in home care services since the pandemic, other potentially negative consequences, and potential positive consequences such as offering of and inclusion in more internet-based social activities or telehealth medical services. The phone survey will be the primary method of collecting the information, with the option to complete the survey in person.

A medical chart review will be used for retrieving medical history and COVID-19 medical information when applicable (some Veterans with SCI may not be treated at their VA hospital, but rather at a local non-VA hospital, in which case this medical information may not be available to the study staff). The chart review will consist of information from the Spinal Cord Injury and Disease (SCI/D) National Office for COVID-19, using the “Coronavirus Disease 2019 SCI Screen (COVID-19 SCI Screen)” and other COVID-19-related medical records, if applicable. The medical records of Veterans with SCI may contain the COVID-19 SCI Screen information and will be recorded on the survey. Any additional medical information will be recorded as appropriate.

A follow-up “in-person” visit to update information from the initial survey and to collect blood samples for virus testing, anti-viral antibody, and other immune analyses relevant to the COVID-19 disease will be planned at least one month after the initial survey. The antibody, cytokine, and other immunological analyses at a future date when our country has recovered from this current pandemic will be critical for determining the number of Veterans with SCI who were infected with the virus, the relationship with the signs and symptoms of infection, if any, and the rate of survival in this population sample. There will also be an option to complete the follow-up survey over the phone for participants who do not wish to travel to the local VAs. An option to complete the blood draw in the home will be available through the services of a VA contracted phlebotomist vendor, ExamOne.

The initial survey and follow-up survey, medical chart review, and blood draw are intended to capture the following information:

Questions related to the **direct impact of COVID-19** on Veterans with SCI will be collected by phone interview using Doximity. Doximity allows for a registered physician (or delegate) to log in and set a phone number, such as each local VA Medical Center who would be represented in this study. The person receiving the call sees the VA Medical Center as the caller ID. Participants will also have the option to complete the initial survey by in-person interview.

In Veterans with SCI, the following information will be collected (but not limited to):

- a) The number who are/were diagnosed with COVID-19, determined from the medical records and/or interviews;
- b) The number who presented with symptoms, determined from the medical records and/or interviews;
- c) The type, duration and severity of symptoms, determined from the medical records and/or interviews;
- d) The number who have anti-SARS-CoV-2 antibodies, with testing to be performed at least one month after initial interview (or whenever is deemed safe for an in-person visit to the medical centers); and
- e) The number and characteristics of those who survived.

Questions related to the **indirect impact of COVID-19** pandemic on Veterans with SCI who rely on caregiver assistance and other services that may have been interrupted during the COVID-19 outbreak will be determined via interview.

The following information will be collected (but not limited to):

- a) The number who report any caregiver assistance;
- b) The relationship to the person(s) who provides the assistance (family, friend, aide, healthcare worker, etc.);
- c) The number whose caregivers live with them;
- d) The number whose caregivers travel to their homes;
- e) Adverse health consequences that resulted from reduced or lack of caregiver assistance
 - a. Any clinically relevant/significant health event during the study period, such as: pressure injury, UTI, fracture, or other,
 - b. Lack of access to in-person medical services when requested or needed (in other words-is the overwhelmed healthcare system also affecting their more general access to care?).
- b) Other adverse consequences of the COVID-19 pandemic on persons with SCI, such as:

- a. Wheelchair maintenance/repair interruption,
- b. Prescription renewal interruption,
- c. Social isolation (lack of interactions with others),
- d. Became unemployed, or
- e. Other

Questions related to the potential positive consequences of the COVID-19 pandemic would also be explored for:

- a) Participation in virtual support groups (i.e. chat groups, other)
- b) Participation in virtual exercise/physical therapy programs
- c) Participation in virtual recreation therapy programs, or
- d) Other.

Most of the survey questions have been developed with fixed-format answers, with as few open-ended questions as possible.

C. Methods

Participants: Veterans with SCI who were initially screened for CS #2003 will be contacted to determine willingness to be consented for participation in the survey and medical chart review and to be consented for the follow-up survey and blood draw at least one month from the initial survey.

The goal is to interview as near to 100% of the 400 plus Veterans with SCI as possible. We believe it is possible to recruit as many as 90% (approximately n=381), but to be conservative, we are expecting 80% (approximately n=338). Eighty percent (80%) is realistic because the sites' staff already know these Veterans with SCI, many of whom would be motivated to know if they have anti-SARS-CoV-2 antibody, will have missed their annual physicals during the pandemic, and will already be scheduled, or in the process of scheduling, to visit their VAMC. (In these cases, the CS #2003 staff would coordinate with the SCI/D service whenever possible to schedule both visits at the same time.)

Baseline/Initial Survey: Two survey forms will be used to collect the medical chart information and the responses from the participant. The medical chart review contains SCI-specific questions to record SCI characteristics of the participants. The survey will also record the loss or reduction in home care services and other potentially negative or positive consequences.

Follow-up Visit: After the COVID-19 national crisis has subsided, a follow-up visit (at least one month after the initial survey) will be scheduled at the VA Medical Centers for any of the Veterans with SCI who participated in the initial survey. During this follow-up visit, the participant will have the option to complete a blood draw and follow-up survey. Additionally, any of the over 400 Veterans with SCI who present to the VA Medical Centers who had not received the initial contact and interview would also be eligible to be interviewed in-person and for the blood draw. If participants complete the follow-up survey, they will receive a stipend of \$50. No additional funding is being requested from CSP for this stipend. All costs will remain budget neutral within each site.

Blood collection: A single blood draw for a total of 20.0 mL of blood for the following will be performed:

1. To be analyzed at each site's local VA laboratory:
 - a. One red top tube (6.0 mL) for c-reactive protein (CRP), spun down for serum and separated into 4.0 mL for the local lab and 2.0 mL to be frozen and shipped to the Chair's Office for antibody testing.
 - b. One purple top tube (6.0 mL) for complete blood count with differential (CBC w/Diff) as whole blood (not spun down) for the local lab.
 - c. Note: Each site will need a laboratory agreement to pay for the costs of the CBC w/Diff and CRP tests.
2. To be shipped to the Chair's Office for analyses:
 - a. From the red top tube above, 2.0 mL, frozen serum for antibody testing
 - b. One green top tube (5.0 mL) spun down for plasma and frozen for cytokine testing
 - c. One PAX gene tube (3.0 mL) frozen as whole blood for transcriptional analysis

If participants complete the blood draw, they will receive a stipend of \$50. No additional funding is being requested for this stipend. All costs will remain budget neutral within each site.

There will be an option to complete the blood draw at the participant's home through services provided by a VA contracted phlebotomist vendor. The vendor, ExamOne, will only provide the blood collection service. They will not be engaged in research activities. All questions about the study (other than blood collection visit schedules and blood draw procedures) will be directed to the local site team and/or the Chair's Office. ExamOne will spin down the samples, as appropriate, and deliver them to the local site personnel for freezing or local site lab analysis.

All blood samples will be labeled with the study ID, date and a coded participant ID number. The serum and plasma of each spun down tube and the PAX gene tube with whole blood will be stored in a freezer for shipment to the James J Peters VA Medical Center, Bronx, NY (Chair’s Office). The cytokine testing will include: Interleukin-1 (normal range 0-5 pg/ml); Interleukin-6 (normal range 5-15 pg/ml); Interferon-alpha (normal range 0 to 35 U/L), Interferon-gamma (normal range <8.1 pg/mL), tumor necrosis factor (TNF)-alpha (normal range ≤ 2.8 pg/mL, and TNF-gamma (normal range <10 pg/ml).

The optimum methodology to perform the antibody analyses will be determined in consultation with the VHA Infectious Disease Service and the Clinical Laboratory at the time of sample analysis. In the future, biological values and other clinical data will may be compared to other populations, including Veterans without SCI or non-Veterans with SCI.

Timeline: It is estimated the study staff can complete the initial surveys on screened participants by the end of September 2021. Once the medical centers have re-opened to outpatient visits, the in-person or phone visits for the follow-up surveys and in-person visits for blood draws can be completed by the end of FY21, which is within the timeframe of the completion of CS #2003. An estimated timeline is provided (Table 22).

Table 22. Timeline	FY20 Q3	FY20 Q4			FY21 Q1 to Q4			
	Jun-20	Jul-20	Aug-20	Sep-20	Q1	Q2	Q3	Q4
Administrative approvals ¹	✓							
CIRB submission		✓						
CIRB approval					✓			
Survey development & refinement	✓	✓						
iDatafax form for the survey			✓	✓	✓			
Train CS #2003 staff (via Teams or other)					✓			
Initial surveys and chart review						✓	✓	✓
Follow-up surveys, chart reviews & blood draws							✓	✓
¹ CS#2003 Executive committee and CSP VACO review and approvals								

D. Relevance

This information will be used to inform the VHA of the medical, sociological and/or quality of life impacts from the COVID-19 pandemic on Veterans with SCI who were screened for CS #2003. Specifically, for the medical impact, we will learn about the number in this sample who were

infected, their symptoms (if any) and severity, any associated illnesses, immunological responses, and the number of individuals who recovered and survived. The sociological and quality of life impact of this virus will also be reported, including the interruption of vital services such as caregivers, medical appointments, wheelchair repair, levels of anxiety, and other aspects. We will also learn about any positive occurrences that may be reported such as usage of telemedicine, and more access to online social groups or web-based activities. **Important benefits from this project will be to improve preparedness for future local and/or national disasters in order to protect Veterans living with SCI from untoward exposure and/or loss of services.**

Notes for consideration:

- On the follow-up visit, if the participant has a positive test for anti-SARS-CoV-2 antibodies, we will know that they had the COVID-19 infection at some time in the past (and even could have been asymptomatic); these individuals would be categorized as persons who have survived. If they test negative for anti-SARS-CoV-2 antibodies, then we will know they had not been infected as of the date of the test.
- Some of the Veterans with SCI who participate in the baseline/initial survey will have already been diagnosed with viral infection and/or COVID-19 (many of our institutions already have some Veterans with SCI who have tested positive for the virus). Some Veterans with SCI are being treated for COVID-19 based on severe symptoms and may not have been tested for viral infection by lab diagnostics until after they have been treated. Other individuals with less severe symptoms, that did not require hospitalization, may not have been tested for COVID-19 using lab tests. In these cases, the antibody testing will reveal how many people with SCI in our study sample had the virus.
- If a Veteran with SCI who was screened for our study has died during this time, the information about the death may be in the medical record at that Veteran's VA medical center and we will be able to capture it from chart review. However, it is recognized that information about those who did not survive will be the most difficult to get for many reasons: lack of documentation in the medical record, lack of definitive information about the cause of death, lack of a COVID-19 diagnosis, etc.
- If a Veteran with SCI who participates in the baseline/initial survey dies at some time afterwards, then upon follow-up, we may learn about the death and be able to acquire some of this information from medical records.

- The additional workload to conduct the survey and in-person visit with the blood draw will be able to be continued without interruption to the usual tasks and duties that are required for CS #2003.

E. Limitations

The screened participants for CS #2003 would have met the inclusion criteria for CS #2003. As such, the Veterans with SCI in this survey sample would have tended to be those with more function and, as a result, will be a biased sample. The generalizability for the results would therefore be limited to the demography of this sample.

If some, or all, of the Sites' VA medical centers have not re-opened by next year, the study staff could still complete the follow-up survey and chart reviews from telework. The survey is of value even without the blood draw since identification of adverse and/or positive aspects of the pandemic would be informative for future preparedness for Veterans with SCI.

Considerations for how the blood draws can safely take place will be discussed at that time and may include solutions such as staff in full Personal Protective Equipment (PPE) going to the Veterans home to take the blood sample.

XXI. REFERENCES

1. Glickman, S. and M.A. Kamm, *Bowel dysfunction in spinal-cord-injury patients*. Lancet, 1996. **347**(9016): p. 1651-3.
2. Cornell, S.A., et al., *Comparison of three bowel management programs during rehabilitation of spinal cord injured patients*. Nurs Res, 1973. **22**(4): p. 321-8.
3. Korsten, M.A., et al., *Difficulty with evacuation after spinal cord injury: Colonic motility during sleep and effects of abdominal wall stimulation*. J Rehabil Res Dev, 2004. **41**(1): p. 95-100.

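### Antibody testing of living volunteers cannot determine a rate of survival, and the COVID-19 sub-study's capture of deaths is too passive to supply one

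*Combined protocol and SAP*

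**What the plan says.** All references are to section XX of the combined protocol and SAP, the COVID-19 addition.

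- **XX.B, purpose of the blood analyses.** The antibody, cytokine and other immunological results are to be critical for determining how many were infected, "the relationship with the signs and symptoms of infection, if any, and the rate of survival in this population sample".
- **XX.B, data list.** One item reads "The number and characteristics of those who survived". The same list has no matching item for deaths. The antibody item comes "with testing to be performed at least one month after initial interview".
- **XX.B, frame.** At the hold on March 16, 2020, "more than 400 Veterans with SCI had been screened for participation across 15 VA sites". Table 21 gives 423.
- **XX.C, Participants.** Screened Veterans "will be contacted to determine willingness to be consented for participation in the survey and medical chart review", and likewise for the follow-up survey and blood draw. Any screened Veteran not reached earlier who presents at a medical center may also be interviewed and give blood.
- **XX.D, Notes for consideration.** Of those who test positive for antibodies, "these individuals would be categorized as persons who have survived". For screened Veterans who have died, the notes expect to obtain the information from chart review where the record holds it. For deaths after the initial survey, they expect that follow-up and records may reveal some. They concede that "information about those who did not survive will be the most difficult to get", citing missing documentation, uncertain cause of death and absence of a COVID-19 diagnosis.
- **XX.E, Limitations.** The only bias named is selection toward Veterans with more function.

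**The concern.** A survival rate needs both the infected who lived and the infected who died. Blood testing supplies only the first group. It also finds silent infections among the living that no chart would show, while a Veteran who died cannot be tested and may have no COVID-19 diagnosis on record. The two parts of the denominator are therefore found by methods of unequal sensitivity.

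The plan for finding deaths is weak. It sets no systematic vital-status check, no start or end date, no denominator and no estimator. XX.C presents the chart review as something Veterans are contacted and consented for, and does not say how this works for a Veteran who died before contact. Timing makes this gap matter. The frame is fixed at March 16, 2020, and Table 22 places the initial surveys and chart reviews in FY21 Q2 to Q4; by that table's month labels, Q2 begins in January 2021. Deaths in those nine months or more come before any possible consent. XX.B adds that records from non-VA hospitals may be unavailable.

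XX.B anticipates that mortality may be higher in this population than in the general population, and XX.C foresees later comparison with other populations. An inflated survival figure could give false reassurance.

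**Working it through.** **Plan's own figures.** The 15 site counts in Table 21 sum to 423. Then 0.80 × 423 = 338.4 and 0.90 × 423 = 380.7, which match the 338 and 381 in XX.C. The plan states no survival rate, precision or sample size for survival.

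**Blood-tested group.** Every person tested is alive at the draw, so survivors/tested = 100% for any true fatality. No assumption is needed.

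**Sub-study as a whole.** Let f be the true fatality among the infected, p the share of living infected who are found, and c the share of deaths found. Then

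observed survival = p(1 − f) / [p(1 − f) + c·f].

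This equals the truth, 1 − f, when c = p. It is too high when c < p and too low when c > p.

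The documents give no fatality for SCI. As assumptions I use the two crude ratios from the May 2020 counts in XX.A, and 15% as a higher value:

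- VA: 1,133/13,327 = 8.5%
- US: 99,462/1,697,361 = 5.9%

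With all living infected found (p = 1):

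| Assumed f | True survival | c = 50% | c = 25% | c = 0 |
|---|---|---|---|---|
| 5.9% | 94.1% | 97.0% | 98.5% | 100% |
| 8.5% | 91.5% | 95.6% | 97.7% | 100% |
| 15% | 85.0% | 91.9% | 95.8% | 100% |

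Worked case at 8.5% and c = 50%: 0.915/(0.915 + 0.5 × 0.085) = 0.915/0.9575 = 95.6%. Apparent fatality is then 4.4% instead of 8.5%.

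**Can the bias run the other way?** Set p = 0.80, the participation expected in XX.C, and suppose every death is found (c = 1). Then 0.80 × 0.915 = 0.732, and 0.732/(0.732 + 0.085) = 89.6%, slightly below the true 91.5%. With p = 0.80 and half the deaths found, 0.732/(0.732 + 0.0425) = 94.5%, again too high.

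**Expected number of deaths.** At an assumed 5% infected and 5.9% fatality, 423 × 0.05 × 0.0586 = 1.2. At 20% infected and 15% fatality, 423 × 0.20 × 0.15 = 12.7. With about 1 to 13 deaths, any rate would be imprecise even if every death were found.

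**The case against.** A reader might infer that the sub-study samples only living, consenting Veterans, so that its survival figure must be near 100% by construction. The documents do not support that. XX.D plans to look for deaths in charts and at follow-up, and XX.B assigns the survivor item to the surveys, chart review and blood draw together. The certain 100% belongs to the blood-tested group alone.

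A reader might also infer that the design can only make these Veterans appear to do better. The 89.6% case shows otherwise: if deaths are found more completely than living infections, observed survival falls below the truth. Upward bias is the likelier direction, because the death search is opportunistic while antibody testing adds silent infections among the living, but it is not assured.

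Three further points stand in the plan's favor:

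- It discloses that data on non-survivors are the hardest to get, although not under Limitations.
- XX.D promises a count of those who recovered and survived, not a mortality estimate.
- The lack of a consent waiver for decedents' charts cannot be established. XX.C is silent on the matter, XX.D expects to use such charts, and consent pages are not in the copy reviewed.

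These points narrow the criticism but do not rescue the XX.B sentence, which attaches the rate of survival to the blood analyses without qualification.

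**Conclusion.** The concern holds in limited form. The XX.B sentence is wrong as written: serology in living volunteers can show past infection among those tested and nothing about survival. A survival rate from the whole sub-study would probably be too high by an amount that the plan gives no means to estimate. At an assumed 8.5% fatality with all living infected found, the overstatement runs from zero if all deaths are found, through 4.1 percentage points (95.6 − 91.5) if half are, to 8.5 points if none are.

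The fatality values, infection proportions and capture shares are assumptions. The 8.5% and 5.9% are crude ratios of reported deaths to reported cases and are not specific to SCI. The 80% is expected participation, not a known yield of blood samples.

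The consequence is contained. The introduction to section XX says these questions are unrelated to the main trial's design and outcomes, so no trial endpoint, power calculation or safety rule changes.

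**What to change.** 1. In XX.B, remove survival from what the blood analyses will determine. Report antibody results only as past infection among living participants.
2. Subject to CIRB approval, check VA records for vital status at one fixed end date for every Veteran in Table 21 (423) who was alive at a stated start date, for example the March 16, 2020 hold. The start date is needed because Table 5 puts the first enrollment year in FY17; without it, deaths before the pandemic would be counted.
3. Report the number of all-cause deaths out of that denominator, list COVID-attributed deaths separately, and state how many Veterans have unknown status. Give no post-infection survival rate: all-cause deaths do not estimate one, and the expected number of deaths is too small for precision.
4. State in XX.C how the chart of a Veteran who died before contact will be accessed.
5. Add survivorship bias to XX.E.

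Items 1, 4 and 5 are text edits. Items 2 and 3 cost a CIRB request and one record check per screened Veteran, by staff already assigned to chart review.
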